## **5.2. Inclusion – Exclusion Criteria and General Study Population**

The general study population will include a total of 240 subjects with POAG or OHT. The inclusion and exclusion criteria defined in the protocol apply to all subjects and are not repeated herein the SAP. Reference is made to the final protocol for the specific inclusion and exclusion criteria for study subjects.

## **5.3. Randomization and Masking**

A total of 240 eligible subjects will be randomized in a 1:1:1:1 ratio into 1 of 4 treatment arms and receive 1 drop in each eye BID, morning, and evening, for 84 days:

- BTQ-1901-A (nebivolol 0.5% ophthalmic suspension) (N = 60)
- BTQ-1901-B (nebivolol 1.0% ophthalmic suspension) (N = 60)
- BTQ-1902 (timolol 0.5% ophthalmic suspension) (N = 60)
- Timolol 0.5% ophthalmic solution (N = 60) [active comparator]

A randomized block design will be used, and the randomization will be created by a biostatistician independent of the trial. Randomization will not be stratified by any factors.

If subjects meet eligibility criteria at Visit 1/Screening as well as at Visit 3/Qualification/Baseline, sites will access the Interactive Web Response System (IWRS) to randomize subjects to study treatment and assign the study medication kit to be dispensed. The drug kit and randomization numbers will be recorded in the subject's eCRF. Study medication from the IWRS-assigned kit will be dispensed to the subject after initial dosing at the study site on Day 1 (Visit 3/Qualification/Baseline). The study will be observer masked.

Rules for unmasking a subject for safety reasons are fully described in the protocol and not repeated herein this SAP.

## **5.4. Analysis Variables**

Variables to be analyzed include demographics and baseline characteristics, efficacy variables (IOP values at each timepoint and change from baseline), safety/tolerability variables (adverse events, bilateral ophthalmic examinations, vital signs, rating of drop comfort, and conjunctival hyperemia grading) and PK concentrations.

## **6. SAMPLE SIZE**

The sample size is not based on a formal sample size calculation; this study is planned to provide sufficient data to power the Phase 3 study.

## 7. GENERAL CONSIDERATIONS

### 7.1. Analysis Populations

There will be 4 (four) analysis populations defined for this study.

#### 7.1.1. Intent-to-Treat Population (ITT)

The ITT population is defined as all randomized subjects. Supplemental efficacy analyses will be conducted on the ITT population.

#### 7.1.2. Per-Protocol Population (PP)

The PP population consists of those subjects in the ITT population who were randomized and dosed and had no major protocol deviations. The primary efficacy analysis will be conducted on the PP population. Subjects who are members of the PP population will be analyzed as randomized.

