7.3. Criteria for Withdrawal from the Study/Criteria for Discontinuation of Study Medication

The following are the criteria for considering withdrawal from the study:

- Withdrawal of subject consent. The subject may request for any reason at any time to be withdrawn from the study.
- Subject lost to follow-up.
- The Sponsor terminates the study (see Section 6.4).

If a subject withdraws from the study, the principal reason for withdrawal will be recorded in the electronic case report form (eCRF). Subjects who are withdrawn will not be replaced.

If a study subject fails to attend a study visit at any point during the study period, every effort should be made to keep the subject in the study and conduct all study visits as scheduled; all attempts to contact the subject must be documented. If the subject relocates during the study period, the clinical research organization (CRO), should be contacted to determine if there is a possibility that the subject could continue at another clinical site.

The following are criteria for considering discontinuation from study medication:

- Pregnancy: If a subject becomes pregnant during the study, the subject will be withdrawn from study medication and followed through the conclusion of the pregnancy (Section 9.5.3).
- Adverse event: A clinically significant or serious AE (SAE) that in the Investigator's or Medical Monitor's judgment, suggests that continued administration of study medication is not in the subject's best interests for safety reasons. Additionally, if an AE requires treatment, the Investigator in consultation with the Medical Monitor may determine that study medication should not be concurrently administered with a required concomitant medication.
- Intraocular pressure in either eye >34 mm Hg during the treatment period.
- Subject request: Subject requests to be withdrawn from study medication.

When possible, a decision to discontinue a subject from study medication should first be discussed with the Medical Monitor. If a subject is discontinued from study medication, every effort should be made to encourage the subject to continue to attend study visits to be followed for safety, rather than withdrawing the subject from the study or, failing that, to perform all early discontinuation assessment procedures at the visit the subject is withdrawn (Section 10.5).

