11.3.1.2. Per-Protocol (PP) Population

The PP population consists of those subjects in the ITT population who were randomized and dosed and had no major protocol deviations. The primary efficacy analysis will be conducted on the PP population.

11.3.2. **Safety Population**

The safety population is defined as all randomized subjects who received at least one dose of the allocated study medication. All safety analyses will be performed using the safety population.

Demographics and Baseline Characteristics 11.4.

Subject demographic and baseline characteristics will be summarized for all analysis populations. Summary tables will be supported with individual subject data listings.

Efficacy Analysis 11.5.

Efficacy analyses will be performed on the PP population for the primary efficacy endpoint using observed data only. Analysis of the efficacy endpoints will also be conducted with the ITT population.

Efficacy data will be presented in tables of descriptive statistics and frequency distribution. All summary tables will be supported with individual subject data listings.

The efficacy measures (IOP) taken at Visit 3/Day 1 at 8:00 AM, 10:00 AM, and 4:00 PM will serve as baseline.

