All data generated during this study and the medical records/documents from which they originated are subject to inspection by the Sponsor or designee, the FDA, and other regulatory agencies. The Investigator must notify the Sponsor or designee promptly of any inspections scheduled by regulatory authorities.

Upon completion of the study, the clinical monitor will conduct a final visit (closeout) to the site. The objectives of this visit are to ascertain that all regulatory records and reports are complete, verify that the investigational product (IP) and other supplies have been accounted for (returned/destroyed), and ensure that the Investigators are aware of their responsibilities once the study ends.

The Investigator is responsible for permitting the Sponsor or designee direct access to any study documents for monitoring and auditing purposes, for providing adequate space for monitoring, and for addressing any questions or issues that might be raised by the monitor or auditor on a timely basis.

13.6. **Case Report Forms and Study Records**

Data relating to study procedures may be entered by site personnel directly onto eCRFs available in the study's eDC system. When the eCRF is the first place study data are recorded, it will be the source document; exceptions are detailed in the Study Manual. Paper source documents will be retained at the study site when appropriate.

13.7. **Protocol Deviations**

The Investigator should not deviate from the requirements of this protocol except in the event of a medical emergency.

A major protocol deviation is defined as nonadherence to the protocol that involves inclusion/exclusion criteria, affects subject safety, or has the potential to affect the integrity of the data, for example, enrollment of a subject who does not meet key eligibility criteria, or failing to collect data necessary to interpret primary endpoints. All protocol deviations will be reported to the Sponsor by entering the event in the appropriate eCRF page. Protocol deviations should be reported to the IRB in accordance with IRB-specific guidelines. If there is any question as to whether the deviation is reportable, the Sponsor or designee and the IRB should be contacted. If subjects are enrolled in error they may be removed after review by the Medical Monitor, but removal is not required. Major and minor protocol deviations will be defined before unmasking.

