### **7.3.2. Missing Data**

All data recorded on the electronic case report form (eCRF) will be included in data listings that will accompany the clinical study report. All efficacy analyses will be based on observed cases (without imputation). Multiple imputation methods and single imputation methods (e.g., last observation carried forward [LOCF]) will be utilized for sensitivity analyses for select variables.

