#### 7.3.2.3. Missing Baseline Data

Every effort will be made to ensure that accurate baseline information on the subjects is collected. In the event that a subject is missing baseline information the subject will be included in the safety population for assessment of safety and excluded from the primary analyses. All baseline data will be observed cases, without imputation.

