### **8.2. Protocol Deviations**

Major protocol deviations, as determined by a Sponsor masked review of the data prior to database lock and unmasking of the study, may result in the removal of a subject's data from the PP Population. The Sponsor or designee will be responsible for producing the final deviation file; this file will include a description of the protocol deviation and clearly identify whether or not this deviation warrants exclusion from the PP Population. This file will be finalized prior to database lock.

All protocol deviations will be presented in a data listing, with a flag to indicate if a deviation was considered major and resulted in the exclusion of the subject from the PP Population. A summary table will be generated based on the classification of protocol deviations.

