## 9. EFFICACY ANALYSES

Unless otherwise noted, all efficacy analyses will be completed using PP and ITT Populations. All efficacy analyses will be completed using the planned dose that the subject was randomized to.

Efficacy data will be presented in tables of descriptive statistics and frequency distribution. All summary tables will be supported with individual subject data listings.

In general, and unless otherwise noted, data summaries will be presented by treatment.

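### Does the per-protocol definition drop subjects from the primary analysis because a post-baseline IOP reading is missing?

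*SAP*

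**What the plan says.** SAP 7.1.2 makes the per-protocol (PP) set the primary efficacy set and words membership without exceptions: "The PP population consists of those subjects in the ITT population who were randomized and dosed and had no major protocol deviations". Protocol 11.3.1.2 uses the same test, "randomized and dosed and had no major protocol deviations".

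Protocol 13.7 describes a major deviation as nonadherence that touches eligibility, safety or data integrity. One of its examples is "failing to collect data necessary to interpret primary endpoints". It adds that the major/minor classification is settled before unmasking.

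SAP 8.2 is softer. A major deviation "may result in the removal of a subject's data from the PP Population". The same section requires a final deviation file that records, for each deviation, whether it justifies leaving the subject out of PP. That file comes from a masked sponsor review and is closed before database lock.

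On missing values, SAP 7.3.2 bases efficacy analyses on observed cases without imputation. SAP 7.3.2.3 says a subject without baseline data is kept "for assessment of safety and excluded from the primary analyses". SAP 7.3.2.4 sets out last-observation-carried-forward and multiple imputation for missing post-baseline values in the sensitivity analyses. SAP 9 states that, unless noted otherwise, "all efficacy analyses will be completed using PP and ITT Populations", and SAP 9.3 repeats the primary model on the ITT set.

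**The concern.** Two of these texts do not fit together. Under SAP 7.1.2 a major deviation always excludes; under SAP 8.2 it may or may not. If uncollected endpoint data counts as major, the stricter text removes a subject for a gap in any of the nine post-baseline readings, although a repeated-measures model can use the readings that remain. No sentence says how many missing readings, or which ones, lead to exclusion.

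Two harms would be possible. If gaps are unrelated to response, usable data are thrown away and the confidence intervals widen. If gaps follow poor response and are more common on the test product, the subjects doing worst leave the primary set and the estimate moves toward noninferiority. A link to response is conceivable because Protocol 7.3 lists this among the criteria for considering a stop of study medication: "Intraocular pressure in either eye >34 mm Hg during the treatment period".

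**Working it through.** The plan has no figure to reproduce. SAP 6 says the sample size was not formally calculated, and neither document gives an SD, a dropout rate or a missing-data rate. The question is mainly one of reading; the numbers below only give scale.

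**Reading the texts together**

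- Protocol 13.7 requires nonadherence, and its example concerns data needed to interpret the primary endpoints. One absent reading out of nine, in a model built for incomplete series, does not clearly qualify.
- Protocol 11.5 plans the primary analysis on PP using observed data only, and SAP 7.3.2 agrees. If every gap removed the subject, PP would hold only complete series and that provision would have almost nothing to act on.
- Stopping study medication for a listed criterion follows the protocol. Protocol 7.3 asks that such subjects keep attending visits, and Protocol 10.5 asks for all Visit 6 procedures, which include IOP.
- The deviation file in SAP 8.2 needs a yes/no exclusion decision for each deviation. That step would be pointless if every major deviation excluded automatically.

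**Precision if the strict reading were applied**

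Inputs: n = 60 per arm (Protocol 6.2). Assumed: SD 3.5 mm Hg, and a chance p of missing a whole visit, independent over three visits. Keeping observed readings leaves n(1−p) per time point; dropping any subject with a missed visit leaves n(1−p)³. Half-width = 1.96 × SD × √(2/n).

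| p | kept n | half-width | strict n | half-width |
|---|---|---|---|---|
| 2% | 58.8 | 1.265 | 56.5 | 1.291 |
| 5% | 57.0 | 1.285 | 51.4 | 1.353 |
| 10% | 54.0 | 1.320 | 43.7 | 1.467 |

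At p = 5% the strict rule drops 60 × (1 − 0.95³) = 8.6 subjects per arm and discards 540 × (0.95 − 0.95³) = 50 valid readings of the 540 planned. Power for the 1.5 mm Hg margin at one time point, with no true difference, is 63% kept and 59% strict.

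Single readings missing independently at 2% are a harsher case: 1 − 0.98⁹ = 16.6% of subjects have a gap, and 60 falls to 50.

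**Bias if the strict reading were applied**

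If excluded subjects run higher by a fixed amount, the PP difference shifts by (excess exclusion rate) × (that amount).

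A simulation gives the consequence. It used two arms of 60, nine time points, correlation 0.6, residual SD 2.5/3.0/3.5 mm Hg and 6,000 trials per case. Stoppers left after Day 15 or Day 42 with equal chance, and the covariance was unstructured. Entries are the percentage of trials meeting the full rule (upper limit below 1.5 at all nine time points and below 1.0 at five or more), in that SD order.

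| Stoppers, test vs comparator | Shift (mm Hg) | True difference (mm Hg) | Strict | Kept |
|---|---|---|---|---|
| 5% vs 3%, +5 mm Hg | 0.02 × 5 = 0.10 | 1.0 | 0.8/0.7/0.5 | 0.7/0.4/0.3 |
| 8% vs 3%, +8 mm Hg | 0.05 × 8 = 0.40 | 1.0 | 7.0/3.9/2.8 | 1.4/0.7/0.7 |
| 11% vs 3%, +10 mm Hg | 0.08 × 10 = 0.80 | 1.0 | 29.6/18.7/10.5 | 1.6/1.3/0.9 |
| 5% vs 5%, +8 mm Hg | 0 | 1.0 | 0.6/0.5/0.3 | 0.8/0.7/0.6 |
| 5% vs 5%, +8 mm Hg | 0 | 0 | 51.1/31.9/19.7 | 39.3/26.5/18.0 |

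The second and third rows favour keeping the readings. They assume that every high-running stopper is excluded from PP, which the texts do not establish. In the first row the two rules barely differ. The fourth shows no reduction in false passes, and the last shows a cost, because the retained high readings add variance.

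With missingness unrelated to response and no true difference (3,000 trials per case), 2% of whole visits missed gives 52/32/20% strict and 54/34/21% kept. Missing 2% of single readings gives 45/26/15% strict and 56/34/21% kept.

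**The case for a change.** The strongest case for acting is that the categorical definition in SAP 7.1.2, the example in Protocol 13.7 and the permissive wording in SAP 8.2 cannot all be applied as written, and that SAP 3.3 nonetheless declares the plan consistent with the protocol. Masking stops reviewers choosing exclusions by arm, but not exclusions that follow outcome. ITT is labelled supplemental, and no sentence says how a PP pass with an ITT failure would be described. The remedy would be a few words.

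Part of this stands. The wording mismatch is real, there is no explicit threshold for missing readings, and masking does not remove selection on outcome. If the strict reading were adopted and poor responders were excluded much more often on the test product, the primary result could mislead, as the 0.40 and 0.80 mm Hg rows show.

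The step from mismatch to harm does not stand. It needs a reviewer to class protocol-permitted stops or isolated gaps as nonadherence and then to record each one as warranting exclusion, against a plan that calls for observed-case analysis. A description rule for discordant results would relabel output already planned: SAP 9.1 displays the differences with 95% intervals and SAP 9 runs the analyses on ITT too, so anyone can set those limits against 1.5 and 1.0 mm Hg.

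**Conclusion.** No change is called for. The difference between SAP 7.1.2 and SAP 8.2 is loose drafting. A cross-reference would be tidier, but the masked review has to make each decision with or without it, and the observed-case plan points that review toward keeping subjects with isolated gaps. The documents do not show that following the plan loses these readings or biases the result, and the ITT model retains them in any case.

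Loosening PP further is a trade-off. It helps if missingness is unrelated to response, or related to response and unequal between arms. It costs up to 12 percentage points of pass probability (51% to 39%) in the balanced case, and it does not reduce false passes there. All these sizes rest on assumed SDs, correlation, missing rates and pressure gaps; none comes from the documents. In a Phase 2 trial with no formal sample size, meant to inform Phase 3 and reporting ITT beside PP, this does not justify amending the plan.

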#### 7.1.3. Safety Population (SAF)

The safety population is defined as all randomized subjects who received at least one dose of the allocated study medication. All safety analyses will be performed using the safety population. Subjects who are members of the safety population will be analyzed as treated.

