8.5. Study Medication Materials and Management

8.5.1. Packaging and Labeling

Study medication will be packaged and labeled at a central packaging facility. Study sites will utilize the IWRS to assign kits to subjects. Each kit has 3 boxes (subkits). Contents of the boxes

(subkits) will differ depending upon treatment allocation (either 5 mL multidose bottles or 10 mL multidose bottles).

- Box 1, dispensed at Visit 3/Qualification/Baseline, includes either 1 bottle (5 mL) of BTQ-1901-A, BTQ-1901-B, BTQ-1902 OR 1 bottle of timolol 0.5% (10 mL)
- Box 2, dispensed at Visit 4/Day 15, includes either 2 bottles (5 mL each) of BTQ-1901-A, BTQ-1901-B, BTQ-1902 OR 2 bottles of timolol 0.5% (10 mL)
- Box 3, dispensed at Visit 5/Day 42, includes either 3 bottles (5 mL each) of BTQ-1901-A, BTQ-1901-B, BTQ-1902 OR 3 bottles of timolol 0.5% (10 mL)

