#### 7.1.4. Pharmacokinetic Population (PK)

The PK population will consist of the subjects who were randomized, dosed, and have at least one PK value. It is planned that plasma concentration will be measured in a subset of 40 subjects. Subjects who are members of the PK population will be analyzed as treated.

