## 10. SAFETY ANALYSES

All Safety analyses will be conducted using the Safety population. Categories for data presentation and analysis will consist of each treatment group (BTQ-1901-A, BTQ-1901-B, BTQ-1902, timolol 0.5%) and overall treatments summary. All safety analyses will be completed using the actual treatment a subject received.

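### As worded, the safety population leaves out a subject who took only another arm's product, so as-treated grouping can act only on mixed exposure

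*SAP*

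**What the plan says.** **Membership.** SAP 7.1.3 admits only randomized subjects who "received at least one dose of the allocated study medication". Protocol 11.3.2 and the statistical methods part of the synopsis define the set in the same way: "all randomized subjects who received at least one dose of the allocated study medication".

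**Scope.** SAP 7.1.3 continues: "All safety analyses will be performed using the safety population". SAP 10 repeats this for the safety section. The population is also the basis for the concomitant medication summaries (SAP 8.5), the compliance summaries (SAP 8.6) and the medical history percentages (SAP 8.4).

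**Grouping.** SAP 7.1.3: "Subjects who are members of the safety population will be analyzed as treated". SAP 10: "All safety analyses will be completed using the actual treatment a subject received". The protocol states no grouping rule for safety.

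**Neighbouring definitions.** For pharmacokinetics, SAP 7.1.4 says: "The PK population will consist of the subjects who were randomized, dosed, and have at least one PK value". The per-protocol definition in SAP 7.1.2 likewise asks for randomization and dosing, plus the absence of major deviations. Neither requires that the dose was of the allocated product.

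**The concern.** An as-treated rule exists mainly for the subject who was randomized to one product and took another. Here the membership test comes first, and it asks for a dose of the randomized product. A subject who took only a different product fails it, so the as-treated rule never reaches that subject.

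The situation is conceivable. Boxes look alike (Protocol 8.2), and the three investigational products come in identical 5 mL bottles (Protocol 8.1), so packaging would not reveal a swap among those arms. A subject could receive the wrong kit at Visit 3 and stop before it was noticed, or the error could go unnoticed throughout.

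At stake is the completeness of the safety summaries. Protocol 4 describes the trial as first in human, and Protocol 5.1 makes ocular and systemic safety part of the primary objective. An adverse event in such a subject would not be counted under the product that the subject actually took.

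**Working it through.** The documents state no figure on this point, so the check is to apply the two SAP 7.1.3 rules to every possible dosing pattern.

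**Step 1: what allocated means.** Protocol 8.5.1, on box contents, has the words "subkits) will differ depending upon treatment allocation", and it then gives the contents by arm. Allocation is therefore the randomized arm, and the allocated medication is that arm's product.

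**Step 2: apply membership, then grouping.**

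| Pattern | Products taken | In safety population as worded? | Group | If membership needs a dose of any study product |
|---|---|---|---|---|
| a | Allocated only | Yes | Allocated product | No change |
| b | Allocated and another arm's | Yes | As treated, but the SAP does not say which product decides | Membership unchanged; grouping still has to be stated |
| c | Another arm's only | **No, although exposed** | None | Enters under the product taken |
| d | None | No | None | No change |

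Pattern c is where as-treated grouping would give an unambiguous reassignment, and the membership rule removes it. In pattern a the grouping rule changes nothing. It has work to do only in pattern b, for which the SAP gives no detail.

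**Step 3: compare with the other populations.** A pattern c subject belongs to the ITT population. If sampled, the subject also belongs to the PK population, analysed as treated. If the error were not classed as a major deviation, the subject would be in the per-protocol population too, analysed as randomized. The safety population would be the only one whose definition itself turns on which product was taken.

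**Step 4: size per subject.** The planned arm size is 60 (Protocol 6.2).

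- One pattern c subject: 1/60 = 1.7% of an arm.
- Three such subjects in one arm (an assumption, to show a range): 3/60 = 5.0%.
- If there are none, nothing changes.

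**The case against.** **The intent is visible.** The SAP says twice that safety follows actual treatment, and a programmer might take *allocated* to mean the kit that IWRS assigned and the site dispensed. This has some force: exclusion follows from the literal text, and it is not certain that the tables would be built that way. It does not remove the problem, because Protocol 8.5.1 ties allocation to the arm and nothing in either document expressly includes a pattern c subject.

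**The two rules do not contradict each other.** A reader might infer that they do. One sets membership and the other sets grouping; both can be applied together, and grouping still operates on mixed exposure. What is left is a gap for one dosing pattern.

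**The data would not vanish.** A reader might also infer this. SAP 7.4.1 and 10.5 put all collected data in listings, SAP 8.2 lists all protocol deviations, and SAP 10.2.1 requires a listing and narratives for all deaths. Serious adverse event reporting under Protocol 9.5.4 does not depend on an analysis population, and the subject stays in the ITT disposition and demographic tables. The loss is confined to summary tables.

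**No probability can be taken from the documents.** An assumed rate of 0.25% to 1% for receiving only the wrong product gives an expected 240 × 0.0025 = 0.6 to 240 × 0.01 = 2.4 subjects. The chance of at least one, 1 − (1 − p)^240, is then about 45% to 91%. The arithmetic is right, but neither document supports that rate. It would have to be the rate of never taking the allocated product at all, which is narrower than any dispensing error. Kits are assigned by IWRS, the first dose is taken at the site, and unmasked staff handle dispensing and accountability, so the true rate may be lower. These percentages should not be read as a forecast.

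**Conclusion.** The point holds on the literal wording, at low severity. As defined, the safety population excludes a subject exposed only to another arm's product, and that subject is then missing from the adverse event, vital sign, eye examination, concomitant medication and compliance summaries. The as-treated rule is left with mixed exposure alone. Each excluded subject would be about 1.7% of a 60-subject arm. How many there would be, if any, cannot be derived from the documents; few or none is the reasonable expectation.

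This rests on reading *allocated* as the randomized arm, which is how Protocol 8.5.1 uses the term, and on the definition being programmed as written. The documents support neither a contradiction between the two rules nor a disappearance of data from the study report.

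**What to change.** In SAP 7.1.3:

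- Define the safety population as randomized subjects who took one or more doses of any study product, whichever arm it belongs to.
- Keep the grouping by treatment actually received.
- Add one sentence on how a subject exposed to more than one product is grouped. Without it, pattern b stays open even after the membership wording is corrected.

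SAP 3.3 now says that the analyses are consistent with the protocol, so record this difference there. Align Protocol 11.3.2 and the synopsis at the next amendment, if there is one. Protocol 13.7 requires any protocol change to go through an amendment, with FDA submission and IRB approval, and this point alone does not call for one.

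The cost is a small SAP edit, to be made before unmasking. Subjects who took only their allocated product, and those never dosed, stay where they are. No efficacy analysis changes.
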